9. ADVERSE EVENT REPORTING

9.1 Definition of an Adverse Event

Any untoward medical occurrence in a patient or clinical investigation subject administered a pharmaceutical product and which does not necessarily have a causal relationship with this treatment. An adverse event (AE) can therefore be any unfavourable and unintended sign (including a clinically significant abnormal laboratory finding), symptom, or disease temporally associated with the use of a medicinal (investigational) product, whether or not related to the medicinal (investigational) product.

9.2 Reporting, Recording and Follow-up of Adverse Events

This study will use the International Common Terminology Criteria for Adverse Events (CTCAE), version 5.0, for adverse event reporting.

For all AEs, relationship to study drug will be reported on the appropriate AE eCRF page. The PI must judge whether the study drug caused or contributed to the AE in which case it is considered to be an adverse drug reaction, and report it as either:

Related (definitely, probably or possibly): there is a reasonable possibility that the study drug caused or contributed to the AE; this conclusion may be supported by the following observations, though these are not required for the determination of relatedness:

- There is a plausible time sequence between onset of the AE and study drug administration;
- There is a plausible biological mechanism through which study drug may have caused or contributed to the AE;

Not related: It is highly unlikely or impossible that the study drug caused or contributed to the AE; this conclusion may be supported by the following observations, though these are not required for a determination of not related:

- another cause of the AE is evident and most plausible;
- the temporal sequence is inconsistent between the onset of the AE and study drug administration; a causal relationship is considered biologically implausible.

All AEs and SAEs occurring after initiation of study drug, regardless of relationship to intervention, will be reported from time of first dose until 30 days after the last dose of study drug or until the initiation of another anti-cancer therapy, whichever occurs first. After this period, investigators should report any serious adverse events that the investigator believes have at least a reasonable possibility of being related to the investigational product.

The investigator should follow each adverse event until the event has resolved to baseline grade or better or is assessed as stable by the investigator or until the patient is lost to follow-up or withdraws consent. Every effort should be made to follow all serious adverse events considered related to study drug or study-related procedures until a final outcome can be reported.

During the study period, resolution of adverse events (with dates) should be documented on the Adverse Event electronic Case Report Form (eCRF) and in the patient's medical record to facilitate source data verification. If, after follow-up, return to baseline status or stabilization cannot be established, an explanation should be recorded on the Adverse Event eCRF.

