12. History of organ allograft transplantation or autologous stem cell transplantation \leq 3 months prior to the first dose of study drug. Patients who received prior CAR-T or other T-cell targeting treatment (approved or investigational) \leq 4 weeks prior to study drug administration
13. Evidence or history of bleeding disorder, i.e. any hemorrhage / bleeding event of CTCAE Grade $>$ 2 within 4 weeks before the first dose of study drug
14. Serious, non-healing wound, ulcer, or bone fracture
15. Previous or concurrent cancer that is distinct in primary site or histology from the cancer being evaluated in this study, with the exception of the following previous or concurrent cancer types:
 - Curative treatment for localized cancer completed without signs of recurrence and treatment-related toxicity and low risk of recurrence as assessed by the investigator,
 - *In-situ* prostate cancer, Gleason Score $<$ 7, prostate-specific antigen $<$ 10 ng/mL (very low risk and low risk, according to therapy guidelines, e.g. the National Comprehensive Cancer Network guideline; active surveillance / observation is a recommended option).
16. Any clinical condition that is considered unstable or might jeopardize the safety of the patient and his / her compliance in the study
17. Inability to swallow oral medications
18. Any malabsorption condition
19. Breastfeeding. Female patients must not breastfeed during treatment and until 4 months after last study drug administration.
20. Treatment with anticancer chemotherapy or immunotherapy during the study or within 3 weeks before the first dose of study drug. For small-molecule drugs, a period of at least 3 half-lives before the first dose of study drug is acceptable. Mitomycin C or nitrosoureas should not be given within 6 weeks before the first dose of study drug.
21. Treatment with systemic steroids (prednisone dose \geq 10 mg/day or equivalent dose).
22. Acute toxic effects (CTCAE Grade \geq 2) of previous anticancer chemotherapy or immunotherapy that have not yet stabilized or if significant post-treatment toxicities have been observed. (Note however that toxic effects of previous anticancer therapy considered as chronic, such as chemotherapy-induced neuropathy, fatigue, alopecia, or anorexia of CTCAE Grade $<$ 2, for which further resolution is not expected, do not prevent participation in this study.)

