- b. Documentation of the primary diagnosis using the complete pathology report. Collection of baseline FLIPI, IPI, or MIPI scores for FL, DLBCL, and MCLC, respectively. Collection of staging information for patients with B-cell lymphoma.
- c. This scan should only be performed for NHL patients and is optional (i.e. not required for patients with other histologies). If a PET-CT is performed at screening, it should be repeated once after the sixth cycle if no progressive disease is detected during the course of treatment and / or to confirm complete response or disease progression.
- d. Collection of screening fresh tumor biopsy will be optional for patients enrolled in whom an archival biopsy is older than 6 months. The tumor biopsy will be obtained before the first dose of study drug (during the screening period when all other general screening procedures have been completed and patients are eligible for study treatment).
- e. Hematology includes CBC + differential (i.e. hemoglobin erythrocytes, leukocytes, platelets, MCV, RDW, hematocrit, neutrophils, lymphocytes, monocytes, eosinophils, basophils, immature granulocytes, nucleated RBCs).
- f. Blood chemistry includes: sodium, potassium, chloride, bicarbonate or total CO₂ (as per site practice), calcium, phosphate, magnesium, total protein, albumin, glucose, serum creatinine, urea, uric acid, total bilirubin, ALT, AST, LDH, alkaline phosphatase, lipase
- g. Virology includes: hepatitis B surface antigen (HBsAg), hepatitis B surface antibody (anti-HB-sAb), and hepatitis C virus antibody (anti-HCV)
- h. Only for women of reproductive potential (including women of reproductive potential whose partners are sterilized).
- i. CT of the relevant disease region for solid tumors and CT thorax, abdomen, pelvis \pm neck for NHL. Patients with neurological symptoms should undergo a CT or MRI brain to rule out brain metastases. The overseeing physician can use their judgement to choose the appropriate scan type to perform.
- j. A full physical exam is required at baseline/screening. The exam should review all body systems as follows: general appearance, respiratory, cardiovascular, abdomen, skin, head and neck, lymph nodes, thyroid, musculoskeletal, neurological, and if clinically indicated, any other systems (investigator to specify). Thyroid exams may be included as part of the head and neck review. If the review of head and neck is normal, the thyroid can also be considered normal.

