8.2 Populations for Analyses

Table 8-1: Analysis Populations

Population	Description
Efficacy	All participants who received at least one dose of PCLX-001 and had at least one on-treatment tumour assessment will be included in the efficacy analysis.
Safety	All participants who received at least one dose of study treatment, whether prematurely withdrawn from the study or not, will be included in the safety analysis.
MTD-determining population (Part A only)	All participants from the safety analysis population who follow the protocol-specified dose regimen within the DLT observation period and have undergone the scheduled safety evaluations, or who discontinued earlier due to a DLT, will be included in the MTD-determining analysis.
Pharmacokinetic	All participants who have received at least one dose of study treatment and who have data from at least one post-dose sample will be included in the PK analysis population. Participants will be excluded from the PK analysis population if they significantly violate the inclusion or exclusion criteria or deviate significantly from the protocol or if their data are unavailable or incomplete, which may influence the PK analysis. Excluded cases will be documented together with the reason for exclusion.

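### AE and SAE reporting opens at the first dose, so a serious complication of the pre-dose research biopsy is not clearly reportable

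*Combined protocol and SAP*

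**What the plan says.** Section 9.2 sets the reporting window: "All AEs and SAEs occurring after initiation of study drug, regardless of relationship to intervention, will be reported from time of first dose". The window closes 30 days after the last dose, or when another anti-cancer therapy starts if that is earlier. The one stated extension runs forward in time and concerns events linked to the study drug: "After this period, investigators should report any serious adverse events that the investigator believes have at least a reasonable possibility of being related".

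On the biopsy, footnote d to Table 7A (section 7.1) says: "The tumor biopsy will be obtained before the first dose of study drug". The table puts it in the column for 7 (±3) days before dosing. The footnote adds that the other general screening procedures are by then complete and the patient is eligible. Section 7.5.1 limits the offer to patients whose archival biopsy is older than 6 months and gives the purpose as response prediction and exploratory research. Under section 7.2.1, consent comes before any screening procedure.

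The safety population in Table 8-1 (section 8.2) is "All participants who received at least one dose of study treatment, whether prematurely withdrawn from the study or not".

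One further sentence of section 9.2, given here without its last word, reads: "Every effort should be made to follow all serious adverse events considered related to study drug or study-related procedures until a final outcome can be". The section therefore expects procedure-related SAEs to exist in the safety data.

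**The concern.** The only scheduled procedure that samples tissue lies wholly before the point at which reporting begins. Its early complications, such as bleeding, can occur before the window opens. No section sets a reporting rule for the interval from consent to first dose.

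The biopsy is done for research, in patients who have otherwise been found eligible. Exclusion 13 in section 4.2 covers "Evidence or history of bleeding disorder, i.e. any hemorrhage / bleeding event of CTCAE Grade" above 2 within 4 weeks before the first dose, and Table 7B rechecks eligibility on Cycle 1 Day 1. A serious bleed could therefore delay or prevent a patient's treatment without the protocol clearly requiring a 24-hour report, and with no listing in which it would appear. At stake is whether the sponsor and safety monitoring team reliably learn of harm from a research-only procedure. Drug toxicity rates are not affected.

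**Working it through.** The plan gives no figure to reproduce. The check is to put the relevant rules on one timeline and then see whether any other text fills the gap.

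**Timeline**

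| Step | Source | In the 9.2 window? | In the safety population? |
|---|---|---|---|
| Consent | 7.2.1 | No | No |
| Optional fresh biopsy, 7 (±3) days before dosing | Table 7A, footnote d | No | No |
| First dose | 9.2; Table 8-1 | Opens here | Entered here |
| Last dose + 30 days, or new anti-cancer therapy if earlier | 9.2 | Closes here | Yes |

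Three cases follow for a serious biopsy complication:

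1. Onset before dosing, patient never dosed: outside the window and outside the safety population.
2. Onset before dosing, patient dosed later: the patient is in the safety population, but the event predates the window.
3. Onset after the first dose (for example a delayed infection): inside the window, and reportable whatever its cause.

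The gap is cases 1 and 2.

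**Does other text close it?**

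- Section 9.3.1 requires all SAEs to be reported within 24 hours and gives no start date. But the AE definition in 9.1 refers to a subject who has been given a pharmaceutical product, the SAE definition in 9.3 refers to an occurrence at any dose, and the initial report is to contain the study drug dose and dates. It is unclear whether this reaches an undosed patient.
- The follow-up sentence in 9.2 covers procedure-related SAEs, but the only causality judgement that section asks for is relationship to study drug.
- Table 7A schedules open AE questioning in the same pre-dose column as the biopsy, and section 11.1 provides a case report form for every consented patient. The information can be gathered and there is somewhere to put it, but neither passage is a reporting rule.
- Section 10.5 allows accrual to be held for significant safety concerns, which could include a biopsy injury, but only if someone has been told of it. Its other triggers concern drug-related events or DLTs.

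These passages pull in different directions, and none sets a rule for the period from consent to first dose.

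**Rough size**

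The documents give neither the number of biopsies nor a complication rate. As an illustration, expected serious complications = N × u × p, where N is participants, u the share of all participants biopsied and p the serious complication rate. Section 8.1 gives N from 9 + 40 = 49 to 52 + 40 = 92. The values u = 20% to 50% and p = 1% to 3% are assumptions, not figures from the documents.

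- N = 49: 49 × 0.20 × 0.01 = 0.1, to 49 × 0.50 × 0.03 = 0.7.
- N = 92: 92 × 0.20 × 0.01 = 0.2, to 92 × 0.50 × 0.03 = 1.4.

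These counts include case 3, which is already reportable, and to that extent overstate the gap. They leave out biopsied patients who never become participants, and to that extent understate it.

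**The case against.** The strongest reply is that the documents are ambiguous rather than closed. Section 9.3.1 asks for all SAEs, 9.2 mentions study-related procedures, Table 7A asks about AEs before dosing, and every consented patient has a case report form. Section 10.3 also provides for a separate safety monitoring plan, which is not among these documents. A diligent site could well report a biopsy complication under 9.3.1. This stands: the defect is an inconsistency in what is required, and such events are not shut out of the record.

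It can also be said that a first-dose start and a dosed safety population are sound choices for describing drug toxicity, and that the primary safety objective in section 2 concerns oral PCLX-001, not screening procedures. This also stands, so neither choice is criticised here.

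A reader might go further and infer that the worst cases are lost entirely, that no biopsy complication is reportable, or that the trial report could show no procedural harm whatever happened. The documents do not support this. Complications with onset after the first dose fall inside the window. Exclusion 13 bars dosing only within its 4-week interval, and nothing in the documents forbids a later first dose, after which the patient is in the safety population. The passages above also give sites a basis for reporting.

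Nor is the biopsy the only invasive procedure. Blood is drawn repeatedly, and section 11.2 mentions optional bone marrow results. It is the only tissue sampling in the schedule.

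**Conclusion.** The point holds as a gap in the reporting rule. As written, a serious biopsy complication that starts before the first dose is not clearly required to be reported, and if the patient is never dosed it also has no place in the Table 8-1 safety population. Section 9.2 is inconsistent here with Table 7A, with 9.3.1 and with its own follow-up sentence.

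The textual finding rests on no assumption. The size does: the illustration gives roughly 0.1 to 1.4 serious complications over the trial, on assumed uptake and complication rates, and the true number is unknown and probably very small. Drug toxicity rates, DLT assessment and MTD determination are untouched. This is a minor improvement to patient protection, worth making because it is cheap.

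**What to change.** In section 9.2, keep the first-dose start for general AEs and all-cause SAEs. Add that SAEs related to a study-specific procedure, including the optional fresh biopsy, are reported from signing of consent, within 24 hours on the existing SAE form, whether or not the patient is dosed.

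Bring 9.1, 9.3 and 9.3.1 into line so that the definitions do not depend on dosing for these events. Let the SAE form record that the patient was not dosed in place of study drug dose and dates, and add an item for relationship to study procedure. State that the pre-dose AE questioning in Table 7A feeds this rule.

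List these events separately for all consented patients and leave the Table 8-1 safety population as it is.

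The cost is a short addition to 9.2, matching edits in the three other sections, a minor form change, one listing and a few extra SAE reports, some from patients who fail screening. The existing screening question and case report form supply the data.

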9.3 Serious Adverse Events

Serious adverse events (SAE) as defined by the Good Clinical Practice Guideline is any untoward medical occurrence that at any dose:

- results in death

- is life-threatening (defined as an event in which the subject was at risk of death at the time of the event; it does not refer to an event which hypothetically might have caused death if it were more severe)
- requires inpatient hospitalization or prolongation of existing hospitalization
- results in persistent or significant disability/incapacity
- is a congenital anomaly/birth defect
- is an important medical event (defined as a medical event(s) that may not be immediately life-threatening or result in death or hospitalization but, based upon appropriate medical and scientific judgment, may jeopardize the subject or may require intervention to prevent one of the other outcomes listed in the definition above)

Examples of such events are intensive treatment in an emergency room or at home for allergic bronchospasm; blood dyscrasias or convulsions that do not result in hospitalisation; or development of drug dependency or drug abuse.

SAEs due to progressive disease (including death) should not be reported as SAEs unless the investigator also deems there is a possible contribution of the study drug or intervention. Hospitalization due solely to the progression of underlying malignancy should NOT be reported as a serious adverse event.

9.3.1 SAE Reporting

All SAEs defined as per ICH guidelines and other adverse events must be recorded on case report forms. In addition, all serious adverse events must be reported by using the SAE form and must be submitted to Ozmosis Research Inc.

Serious Adverse Event Reporting Instructions

All serious adverse events must be reported as follows:

Within 24 hours: Report initial information (on trial specific SAE report form) by fax to:

Ozmosis Research Inc.

[contact]

[contact]

The initial information should always contain:

- Name of Reporter/Investigator,
- Subject Identification,
- Adverse Event Term,
- Study Drug Dose and Start/Stop Dates

On the next working day: Fax completed trial-specific Serious Adverse Event form

All follow-up SAE reports should be submitted to Ozmosis as soon as possible.

The PI/Sponsor will be made aware of all Serious Adverse Events within 24 hours. All SAEs will be reported to the local research ethics board (REB) and regulatory authorities, as applicable, in accordance with local guidelines. Health Canada, any collaborating centres and any pharmacovigilance teams (as applicable) will be notified by the Sponsor in an expedited manner of all SAEs which are unexpected and related to the investigational product.

10. MONITORING, AUDITING, AND INSPECTING

The investigator(s)/institution(s) will permit trial-related monitoring, audits, REB, Safety Monitoring, and regulatory inspection(s), providing direct access to paper and/or electronic documentation pertaining to the clinical study (e.g. CRFs, source documents such as hospital

patient charts and investigator study files). Monitoring of this study will be conducted as per the study monitoring plan.

Audits may be conducted by the study sponsor, the sponsor's designate, and/or the jurisdiction appropriate regulatory agencies (e.g Health Canada, the FDA). All site facilities related to the study conduct could be visited during an audit (e.g. pharmacy, laboratory, outpatient department). The investigator agrees to co-operate and provide assistance at reasonable times and places with respect to any monitoring or auditing activity.

10.1 Source Data

The Investigator will maintain accurate source records from which the case report forms are based. The investigator agrees to allow the monitor direct access to all relevant documents

10.2 Quality Control and Assurance

The sponsor / designee will monitor the site activity to verify that:

- The rights and well-being of human participants are protected.
- The reported trial data are accurate, complete, and verifiable from source documents.
- The conduct of the trial is in compliance with the currently approved protocol/amendment(s), with GCP, and with applicable regulatory requirements(s).

10.3 Safety Monitoring Plan

A safety monitoring plan will be established for this study in conjunction with Pacylex Pharmaceuticals, Inc and Ozmosis Research.

Regular meetings will occur prior to dose escalation to monitor the safety aspects of the trial and review safety data. Additional meetings may be scheduled as necessary and if any of the safety stopping rules are met.

10.4 Deviations

The investigator is responsible to identify, document, assess and report all protocol deviations in accordance with Sponsor's, REB's and Health Canada's / the FDA's (as applicable) requirements.

10.5 Safety Stopping Rules

Accrual will be on hold and a meeting held with the principal investigator, investigators and safety monitoring team if the following occurs:

- If there is a death or unacceptable toxicity (SAE or AE grade ≥ 3 .) attributed as: possibly, probably or definitely related to the experimental product.
- If there is a protocol treatment-related Serious Adverse Event (any SAEs deemed by PI to be definitely, probably or possibly related to study drug), or any significant safety concerns
- If the first 2 patients enrolled experience DLT

A decision will be made by the PI and safety monitoring team regarding whether the study will be re-opened for the next patient in the study or not. If there is disagreement in the SAE causality assessment or whether or not to re-open accrual between the different parties, the final decision will rest on the safety monitoring team. Ozmosis Research will notify all sites and applicable parties on the decision and whether accrual has re-opened. Only when it is deemed safe can the next patient start the treatment phase of the study.

